#### Statistical Analysis Plan:

To assess the preliminary efficacy of the Activate program we will examine changes in proximal primary outcomes of average daily active minutes compared between treatment and control groups at baseline and the 12-week follow-up assessment. We will conduct multilevel models with baseline- residualized gain scores for outcomes to identify the effect size for the treatment program on each on the primary outcome. All participants will be used in analyses, with missing data addressed using an intention-to-treat approach where missing data were included and given a zero. A power sensitivity function was generated wherein our pilot study analyses were used to determine expected effect sizes. Anticipated effect sizes based on our pilot work for between group differences in behavior-change skills and average daily active minutes are Cohen's  $d$  of 0.4 to 1.2. With 60 participants, we will have 80% power to detect a Cohen's  $d$  of .7, 60% power to detect a Cohen's  $d$  of .6, at 95% power to detect a Cohen's  $d$  of .8. Thus, we will be powered to detect all but the smallest of potentially meaningful effects found in our previous intervention pilot work.

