Physical Activity Incentives Program. The physical activity incentives program includes 12 weeks of personalized goals and incentives for increasing physically active minutes along with weekday text-based support. Active minutes, defined as minutes with moderate to vigorous physical activity, will be tracked via a Garmin fitness activity tracker, which is synced to a coded study-specific account via PhysioQ's Labfront, a secure site used to collect and manage Garmin fitness activity tracker data. All data will be deidentified and only accessible to the research team. In week 1, all adolescents will receive incentives for syncing their Garmin fitness activity tracker on at least five days. In weeks 2 to 12, adolescents will receive personalized daily and weekly activity goals based on their progress. Daily incentives will be offered for meeting daily goals, and increased earnings will be available for meeting weekly bonus goals. Maximum earnings across the 12 weeks will be \$430. Weekdays, text-based support will be provided to remind adolescents of goals and earning potential as well as additional support to problem-solve technology and physical activity difficulties when indicated. Education prior to the intervention will follow American Diabetes Association³¹ guidance including information about how insulin requirements change with increased physical activity and how to prevent hypo and

hyperglycemia during and after exercise as well as reviewing the adolescent's plans for managing low blood glucose and contacting their pediatric endocrinologist with questions about glucose management with increased physical activity. All incentives will be delivered weekly on a cash card provided by the study or via gift card(s) provided at an interval chosen by the participant.

Treatment-as-Usual Control condition. For those in treatment as usual, participants will be trained to wear a Garmin fitness activity tracker daily for the next 12 weeks and asked to follow their standard care for diabetes management.

Describe required screening procedures performed before enrollment and while on study.

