Behavior-Change Skills. We will use two measures to assess key behavior-change skills taught in the intervention program: goal setting and coping skills. Adolescents' goal setting will be assessed using a procedure by Karoly et al. (2005) that was validated for use with adolescents with type 1 diabetes.^{65,66} Participants will be asked to identify their most important diabetes, academic, social, and career/family goals. Following this, participants will be asked to identify which of their three non-diabetes goals most interfered with their diabetes goal. Participants will also complete the four-item planning subscale from the Goal System Assessment Battery⁶⁵ to determine goal-directed planning activity related to the diabetes goal identified in the goal assessment. Average levels of goal-directed planning will be used as the outcome variable for goal setting. Adolescents' coping skill self-efficacy will be assessed using the Coping Self-Efficacy Scale, a 26-item measure that indexes participants confidence in using different strategies to cope with challenges in daily life.⁶⁷

Active minutes. We will use Garmin fitness activity tracker tracking to determine the average number of daily minutes with moderate to vigorous physical activity, metabolic equivalents (METs) greater than or equal to 3 METs, in week 1 and week 12.

Secondary Biobehavioral Self-Regulation Mechanisms

2. **Self-Report Assessment of Behavior Regulation and Distress:** The self-report tasks will be completed via questionnaires linked only to study ID on RedCap with the access link provided by the research assistant. When noted the parent will also report on their perception of their child's functioning in that domain.

Self-Regulation. We will use the following measures to assess regulation generally and in the diabetes context.

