To assess the preliminary efficacy of the Activate program we will examine changes in proximal primary outcomes of goal-setting, coping skill efficacy, and average daily active minutes compared between treatment and control groups at baseline and the 12-week follow-up assessment. We will conduct multilevel models with baseline-residualized gain scores for outcomes to identify the effect size for the treatment program on each of the three primary outcomes. Each model will include the baseline outcome covariate as well as additional disease covariates including diabetes technology use and length of diagnosis. All participants will be used in analyses, with missing data addressed with full information maximum likelihood estimation. A power sensitivity function was generated wherein our pilot study analyses were used to determine expected effect sizes. Anticipated effect sizes based on our pilot work for between group differences in behavior-change skills and average daily active minutes are Cohen's d of 0.4 to 1.2. With 60 participants, we will have 80% power to detect a Cohen's d of .7, 60% power to detect a Cohen's d of .6, at 95% power to detect a Cohen's d of .8. Thus, we will be powered to detect all but the smallest of potentially meaningful effects found in our previous intervention pilot work.

In aim 2, we test the impact of the Activate program on secondary mechanisms of biobehavioral self-regulation systems and glycemic and cardiovascular disease risk outcomes closely linked with type 1 diabetes health disparities. To assess changes in putative mechanisms and secondary outcomes we will use baseline-residualized gain scores in multilevel models to identify the effect size for the treatment program on each of the secondary outcomes assessed for behavior regulation, distress, c-reactive protein, mean and variability in daily blood glucose, and cardiovascular disease risk score. For all analyses missing data will be addressed with full information maximum likelihood estimation. A power sensitivity function was generated wherein our pilot study analyses were used to determine expected effect sizes. Based on our pilot work we anticipate effect sizes from Cohen's d of .4 to .8 and thus with 60 participants, we will again have 80% power to detect a Cohen's d of .7, 60% power to detect a Cohen's d of .6, at 90% power to detect a Cohen's d of .8. We will be powered to detect all but the smallest of potentially meaningful effects found in our pilot work.

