Should any adverse events, unanticipated problems or reportable new information arise, the PI will contact the IRB according to the Adverse Event and Unanticipated Problems Reporting Policy using the UVM Reporting Form.

Withdrawal Procedures: Define the precise criteria for withdrawing subjects from the study. Include a description of study requirements for when a subject withdraws him or herself from the study (if applicable).

At any time, a participant can choose to withdraw from participation. We do not anticipate withdrawing any adolescent from the study but reserve the right to do so under unforeseen circumstances. These might include situations such as discovery of a medical problem indicating the adolescent should not participate in physical activities. If a participant is withdrawn or withdraws from participation their data will not be included in analyses.

Sources of Materials: Identify sources of research material obtained from individually identifiable human subjects in the form of specimens, records or data. Indicate whether the material or data will be obtained specifically for research purposes or whether use will be made of existing specimens, records or data.

All data is being collected solely for research purposes. Participants will provide dried blood spot assays, measurements of abdominal circumference and blood pressure as well as complete computerized self-report questionnaires. This data will be coded at the time of collection.

DRUG INFORMATION

Investigators are encouraged to consult the UVM Medical Center Investigational Pharmacy Drug Service ([name]) prior to finalizing study drug/substance procedures.

Drug (s)

Not applicable

Drug name – generic followed by brand name and common abbreviations. Availability – Source and pharmacology; vial or product sizes and supplier. If a placebo will be used, identify its contents and source.

Preparation: Reconstitution instructions; preparation of a sterile product, compounded dosage form; mixing guidelines, including fluid and volume required. Identify who will prepare.

Storage and stability – for both intact and mixed products.

Administration – Describe acceptable routes and methods of administration and any associated risks of administration.

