Not applicable

Will the SONA Psychology Pool be utilized? Include documentation indicating permission to use this recruiting tool Yes No

FINANCIAL CONSIDERATIONS

Describe all potential research related expenses to subjects:

There is no expense to participant adolescents or their parents/guardians except for their time required to complete the study and the use of internet to complete the assessment and receive study messages.

Compensation for participation: Describe all plans to pay subjects, either in cash, a gift or gift certificate. Please note that all payments must be prorated throughout the life of the study. The IRB will not approve a study where there is only a lump sum payment at the end of the study because this can be considered coercive. The amount of payment must be justified. Clarify if subjects will be reimbursed for travel or other expenses.

Not applicable

All Adolescents will receive \$25 for the intake assessment and \$50 for the follow-up assessment on a study provided cash card or gift card. Adolescents in the control group will be provided an incentive for wearing their Garmin fitness activity tracker, \$.50/day up to \$42. Adolescents in the intervention group can earn up to \$430 for meeting physical activity goals as a part of the incentives program. This amount is common for incentives programs and meets Medicaid guidelines for \$500 in annual incentives.

Research Data Management Plan: The Research Data Management and Security Plan form must be completed. The form, along with guidance, can be found in our [forms library](#) and must be submitted with your initial application.

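### The documents handle missing active-minutes data in three incompatible ways, and the SAP's zero rule distorts the effect estimate on every reading

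*SAP*

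**What the plan says.** Both documents name average daily active minutes as a primary outcome. The protocol (Primary Outcomes, Active minutes) measures it by Garmin tracker as the "average number of daily minutes with moderate to vigorous physical activity", in week 1 and week 12. Three statements then govern missing values:

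- SAP, Statistical Analysis Plan: all participants are analysed, with "missing data addressed using an intention-to-treat approach where missing data were included and given a zero".
- Protocol, Statistical Considerations: "All participants will be used in analyses, with missing data addressed with full information maximum likelihood estimation".
- Protocol, Withdrawal Procedures: "If a participant is withdrawn or withdraws from participation their data will not be included in analyses".

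The model is described as "We will conduct multilevel models with baseline-residualized gain scores for outcomes", and the SAP describes it in the same terms.

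Reasons to wear and sync the tracker differ by arm. The Physical Activity Incentives Program says "In week 1, all adolescents will receive incentives for syncing their Garmin fitness activity tracker on at least five days". For later weeks it says "Daily incentives will be offered for meeting daily goals, and increased earnings will be available for meeting weekly bonus goals", with a maximum of $430 and weekday text support. Under Compensation for participation, controls are "provided an incentive for wearing their Garmin fitness activity tracker", at 50 cents a day to a maximum of $42.

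**The concern.** The three statements cannot all apply to the same adolescent, and the analyst could choose among them after seeing the data.

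The zero rule is also unsound in itself. A missing tracker value means the device was not worn, not synced, or the participant had left; it does not mean no activity. Intention-to-treat settles who is analysed and gives no reason to enter a zero. The SAP does not say whether the zero is minutes, change from baseline, or the residualised gain it models, nor whether it applies to a whole week or to single unworn days. Neither document defines a valid-wear day. The nearest rule is the week-1 payment for syncing on five days, which is an incentive condition.

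At stake is the quantity the trial sets out to report, the effect size on active minutes. Because the arms have different reasons to wear the device, unequal missingness is plausible, though its direction cannot be predicted.

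**Working it through.** **The rules applied to one case.** Take an adolescent with week-1 data who withdraws in week 6. The SAP keeps the participant with a zero. Statistical Considerations keep the participant and use the available data through the likelihood. Withdrawal Procedures remove the participant altogether. The last is strictly a rule about the analysis set, but it contradicts the statement in both documents that all participants are used.

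**The plan's own figures.** The documents give no missingness rate, mean or SD for active minutes. Their only relevant figure is power: 80% at d = 0.7 with 60 participants, with no stated allowance for missing data. At 30 per arm and two-sided 5% (both assumed), a t-test gives 76.0%, or 79.8% with a baseline correlation of 0.3. That mismatch is a separate matter; nothing below depends on it.

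**Expected estimate under each reading.** Let μ be the control mean, δ the true effect, and mA and mC the missing fractions at week 12 in Activate and control, with values missing at random.

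- Zero minutes: (1 − mA)(μ + δ) − (1 − mC)μ = μ(mC − mA) + δ(1 − mA)
- Zero change: δ(1 − mA)
- Zero residualised gain (pooled regression): 2δ(1 − mA)(1 − mC) / (2 − mA − mC)

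Only the first can be non-zero when δ = 0.

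**Numbers put in.** Assumed: 30 per arm, μ = 40, SD 20 min/day, baseline correlation 0.5, minutes floored at zero, two-sided 5%. False-positive rates and power come from simulated baseline-adjusted analyses, 30,000 trials per scenario. A second simulation with separate code agrees to within about one percentage point.

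Zero minutes, no true effect:

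| Missing, Activate/control | Bias (min/day) | False positives |
|---|---|---|
| 5%/10% | 40 × 0.05 = +2 | 6% |
| 10%/20% | 40 × 0.10 = +4 | 11% |
| 10%/30% | 40 × 0.20 = +8 | 28% |
| 20%/10% | 40 × (−0.10) = −4 | 11% |

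With 30 per arm, 10%/20% is 3 adolescents against 6. Analysing observed values only, which approximates FIML here, gives no bias and 5% throughout. Equal missingness also keeps the level at about 5%.

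Other assumed distributions, for the first three pairs:

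- Mean 30, SD 20: +1.5, +3 and +6 min/day, with 6%, 9% and 23% false positives.
- Skewed (gamma, mean 30, SD 30): 5%, 7% and 14% false positives.

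True effect d = 0.7 (13.9 min/day after flooring), mean 40:

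- Zero minutes, 30%/10%: 40 × (−0.20) + 13.9 × 0.70 = 1.7 min/day.
- Zero minutes, 10%/30%: 40 × 0.20 + 13.9 × 0.90 = 20.5 min/day.
- Zero minutes, equal 10%: power 58%, against 82% for observed data only.
- Zero minutes, equal 20%: power 40%, against 77%. At mean 30, SD 20 it is 47% against 77%; in the skewed case, 59% against 76%.
- Zero change: 13.9 × 0.80 = 11.1 at equal 20% (power 74%); 13.9 × 0.70 = 9.7 at 30%/10% (61%).
- Zero residualised gain: 11.1 at equal 20% (77%); 13.9 × 2 × 0.7 × 0.9 / 1.6 = 10.9 at 30%/10% (76%; simulated estimate 10.8).

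**Day level.** If two unsynced days in seven are scored zero, a true 40 min/day becomes 40 × 5/7 = 28.6.

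**The case against.** The strongest reply is that the harm depends on reading zero as zero minutes. The SAP models residualised gains, so the zero could mean no gain; the false-positive rate then holds at 5% and most power survives. This stands as a limit on the worst figures, but even on that reading the effect is shrunk, to about 11 from 13.9 min/day at equal 20% missing.

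Every size is assumed, and 40 min/day may be high for adolescents recruited for moderate to no activity. At mean 20, SD 15, the zero-minutes bias is about +2 min/day (9% false positives) at 10%/20% and about +4 (20%) at 10%/30%. At 5%/10% the inflation is trivial in every setting. Both arms have some reason to wear the tracker, so the imbalance may be small. All of this is fair, and it affects size rather than the need to fix the rule.

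Two further limits stand. The protocol refers to an attached intervention guide that was not available; it might contain a wear or sync rule. The simulations remove only week-12 values, at random, so missing week-1 values are not covered.

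That the trial is preliminary is a weak defence: both documents say the models are there to identify the effect size, which is what zero scoring distorts.

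**Conclusion.** The concern holds. That the three rules conflict, and that the zero is undefined, follows from the text and needs no assumption. If zero means zero minutes, the bias with no true effect is the mean minutes times the difference in missing fractions. Under the assumptions above that is 2 to 8 min/day at mean 40, and its sign depends on which arm has more missing data. A real effect of d = 0.7 can be almost erased or inflated by nearly half (20.5 against 13.9 min/day). The other two readings protect the false-positive rate but still pull the estimate towards zero. The actual size cannot be known from the documents, which give no mean, SD, correlation or missingness rate. This must be fixed before the primary analysis is run.

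**What to change.** Required:

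1. Delete the zero rule from the SAP. State the protocol's FIML analysis of all randomised participants as primary, in the same words in both documents.
2. Pre-specify a valid-wear definition for weeks 1 and 12 (minimum hours per day and days per week), and treat days or weeks that fail it as missing.
3. Amend Withdrawal Procedures so that data collected before withdrawal are kept, after checking this against what participants agreed to in the consent form.

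Advisable:

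4. FIML assumes data are missing at random, so add one sensitivity analysis that shifts missing values by arm. For example, 20% missing in one arm and 10 min/day lower moves the estimate by 0.20 × 10 = 2 min/day.
5. Report valid-wear days by arm.
6. If zero scoring is kept at all, label it a sensitivity analysis and state what is set to zero.

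Using tracker data from the intervening weeks in the model is optional. The cost is wording in the SAP and two protocol sections, a wear definition and one extra analysis, plus any ethics review the withdrawal change requires. It needs no additional participants, visits or data.
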